1.2 BACKGROUND AND RATIONALE

1.2.1 Glioblastoma

Glioblastoma (GB) is a primary brain tumor and the most common type of gliomas. Although the incidence rate of 3 per 100,000 is relatively low compared to other cancer types, this disease accounts for disproportionately high cancer associated morbidity and mortality due to involvement of the central nervous system and lack of effective therapies([11](#)). The average overall survival of treated GB patients ranges from 8 to 14 months with only 9.8% alive 5 years after diagnosis([12](#), [13](#)); these are figures that have not significantly changed over the past decades in spite of improvements witnessed in surgical and imaging techniques and considerable positive strides made in treatment of other cancers. Median survival after tissue diagnosis without additional treatment is 3 months.

Optimal upfront treatment of GB consists of craniotomy to remove as much tumor tissue as possible, followed by concurrent temozolomide chemotherapy and ionizing radiation. Even for patients exposed to multimodality therapy of craniotomy, chemotherapy, and irradiation, disease recurrence is inevitable; at such time, patients face very limited therapeutic options. This dismal outlook for GB underscores the importance of identifying more effective treatment strategies. Often cited reasons for the refractory nature of GB include: 1) Intrinsic relative resistance of tumors cells to chemotherapy and irradiation; 2) Infiltrating growth pattern of tumor cells into surrounding normal brain that has two clinical consequences: a) precludes surgical removal of all tumor cells; b) tumor cells distant from the surgical margin are spared from exposure to cytotoxic dose of irradiation because radiation to the whole brain results in unacceptable toxicity; 3) Presence of a “protective” blood-brain-barrier (BBB) that prevents efficient entry of exogenously administered polar drugs into the tumor bed. It should be noted that although GB is the most common of the primary brain tumors called gliomas, other gliomas exist in the brain,

Abbreviated Title: Phase II Study LB100 gliomas

Version Date: 06/02/2022

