3 STUDY IMPLEMENTATION

3.1 STUDY DESIGN

This is a two stage Phase II, open label, single institution study to determine the PK and PD profile of LB100 in the setting of gliomas. Patients who are planned for craniotomy will be enrolled if they meet the inclusion criteria. Patients will be admitted to the Clinical Center for the surgery. Tumor tissue will be sampled as part of neurosurgical procedure. LB-100 will be infused over 2 hours (+/- 15 minutes) via IV infusion 2 to 4 hours before surgery. The dose established from a Phase I study will be 2.33 mg/m². Because the tumor resection phase of the craniotomy for

[figure not shown]
Abbreviated Title: Phase II Study LB100 gliomas

Version Date: 06/02/2022

recurrent gliomas typically lasts from one to 5 hours, tumor tissue will be sampled at multiple time points as clinically indicated. The exact time points of tissue removal from LB100 infusion will be recorded by a member of the study team in the OR. Plasma sampling for PK measurements of LB100 will be performed on all participating subjects. (See section **5.1**).

Up to 25 patients may be enrolled to obtain 8 evaluable patients. Five patients will be initially treated. If one of five demonstrates a PK response, 3 additional subjects will be enrolled. PK effect will be declared to be significant if at least 2 of the 8 patients demonstrate a PK response (Presence of LB100 in tumor tissue). Participants whose pathology demonstrates treatment effect or not active tumor will be replaced.

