5.1.1.2 Tissue

Tissue PK: Glioma tissue sampling to detect and quantify LB100 will be performed post-dose in each patient as clinically indicated (time points from end of LB100 infusion will be recorded).

The removed tissues will be rinsed with saline immediately (to remove blood that contains LB100 to avoid falsely high measurements) then divided, flash frozen, and placed in a cryo tube. Majority of the tissue will be used for PK analysis. A small aliquot (~100 ug) will be saved in cryo tube for PD evaluation. PK samples will be transported to the Laboratory of [name] (Molecular Pharmacology Section, Genitourinary Malignancies Branch) to quantitate LB100 tissue concentration.

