5.2 SAMPLE STORAGE, TRACKING AND DISPOSITION

5.2.1 Tissue blocks

5.2.1.1 Laboratory of Pathology

Paraffin embedded tissue block will be stored at Laboratory of Pathology located at building 10. Tissues designated for clinical diagnostics are transported to the Laboratory of Pathology (LP) where they are examined grossly and relevant portions are fixed, embedded in paraffin and sectioned and stained for diagnostic interpretation. Unutilized excess tissues are stored for up to three months, in accordance with College of American Pathologists/Joint Commission on Accreditation of Healthcare Organizations (CAP/JCAHO) guidelines, and then discarded. Following completion of the diagnostic workup, the slides and tissue blocks are stored indefinitely in the LP's clinical archives. All specimens are catalogued and retrieved utilizing the clinical laboratory information systems, in accordance with CAP/JCAHO regulations. The use of any stored specimens for research purposes is only allowed when the appropriate IRB approval has been obtained. In some cases, this approval has been obtained via the original protocol on which the patient was enrolled.

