10 STATISTICAL CONSIDERATIONS

The primary objective of this study is to determine the PK response of LB100 in glioma tissue. The PK response is defined as a binary endpoint indicating the presence/absence of LB100, and will be established by measuring the level of LB100 in resected tumor tissues. This two-stage study is designed to define a significant PK effect with an expected target PK response rate of 40% across patients. The expected 40% response rate is based on preliminary in vitro and animal studies.

Up to 25 patients may be enrolled to obtain 8 evaluable patients. Five patients will be initially treated. If one of five demonstrates a PK response, three additional subjects will be enrolled. PK effect will be declared to be significant if at least 2 of the 8 patients demonstrate a PK response. This yields 87% power to detect a 40% PK response rate across patients, with an overall 10% false positive rate under the null hypothesis that the agent has no biologic effect([17](#)).

The PK parameters, including C_{max} , AUC and elimination half-life time $t_{1/2}$, will be estimated based on standard PK modeling.

PD response is defined as statistically significant elevation of phospho-protein expression in treated tumor tissues compared to untreated glioma specimens. Tissue samples obtained with the initial surgical exposure of the tumor OR material obtained prior to LB100 infusion will be used as control. Untreated inter-patient baseline variance of phospho-protein expression and standard deviation (SD) will be calculated. Post-treatment PD effect (as measured by increase in tumor tissue phospho-protein expression) difference greater than 2.5 times the baseline SD is statistically significant at the .05 significance level. Due to relatively small sample size, t-

Abbreviated Title: Phase II Study LB100 gliomas

Version Date: 06/02/2022

distribution is to be used to calculate the cutoff defining the PD response. The frequency of PD response and its 95% confidence interval will be estimated.

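### The PD control may be same-operation tissue or pre-infusion material of unstated origin, yet Section 10 sets one baseline SD and one 2.5-SD cutoff for both

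*Combined protocol and SAP*

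**What the plan says.** Section 10 defines a tumor PD response as a significant rise of phospho-protein in treated tumor over untreated glioma. Two kinds of tissue may serve as the untreated control, as alternatives: "Tissue samples obtained with the initial surgical exposure of the tumor", or "material obtained prior to LB100 infusion will be used as control". The source of the second kind is not named, and no rule says which kind applies to which patient. The section goes on: "Untreated inter-patient baseline variance of phospho-protein expression and standard deviation (SD) will be calculated". It adds that a post-treatment "difference greater than 2.5 times the baseline SD is statistically significant at the .05 significance level", with a t distribution used for the cutoff. It does not state the number of controls, the degrees of freedom, the sidedness, or whether a treated sample is compared with the patient's own control or with the control mean.

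**Timing.** Section 3.1 says: "LB-100 will be infused over 2 hours (+/- 15 minutes) via IV infusion 2 to 4 hours before surgery". The calendar in Section 3.4 marks LB100 under pre-treatment, and Section 3.7.2 speaks of exposure before surgery. Section 5.1.1.1, however, lists the pre-dose and end-of-infusion blood samples among those that may be drawn during the operation. Section 5.1.2.11 plans to assay tumor removed both before and after the infusion.

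**Tissue.** Under Section 5.1.1.2 the sampled tumor is rinsed, "then divided, flash frozen, and placed in a cryo tube". For the diagnostic archive, Section 5.2.1.1 says: "Paraffin embedded tissue block will be stored at Laboratory of Pathology located at building 10". Section 2.2.1 asks for slides from the latest earlier biopsy or resection, for diagnostic review. Section 1.2.1 describes upfront glioblastoma surgery as "followed by concurrent temozolomide chemotherapy and ionizing radiation".

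**The concern.** A PD contrast is interpretable when control and treated tissue differ in LB100 exposure and little else. On the Section 3.1 timing, the study craniotomy yields no pre-infusion tumor, and the documents describe no separate pre-infusion biopsy. Pre-infusion material must then predate the study. Because patients have recurrent disease, therapy may have been given in between, storage time differs, and preservation may differ too. The rule would read the whole difference as drug effect.

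The second risk is mixing. If some patients contribute earlier tissue and others same-operation tissue, one SD over all controls includes the gap between the two types, and that SD sets the cutoff for every patient. What is at stake is the PD response frequency (objective 1.1.2.2) and the tumor side of the PBMC correlation (objective 1.1.2.5).

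**Working it through.** **1. Reproduce the 2.5.** Assume n = 8 controls (the evaluable target; the number of controls is not stated) and a t limit for one new value against n baseline values: t(0.975, 7) × √(1 + 1/8) = 2.365 × 1.061 = 2.51. This matches 2.5 at two-sided .05. The one-sided .05 limit would be 2.01. The match assumes one homogeneous set of controls.

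**2. Where the pre-infusion control can come from.**
- Infusion before surgery (Sections 3.1, 3.4, 3.7.2): only an earlier biopsy or resection.
- Infusion during surgery (which Sections 5.1.1.1 and 5.1.2.11 fit): the same operation is possible, with no intervening therapy and the same handling.

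The two sets of sections do not agree, so the meaning of the control is open.

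**3. Effect of mixing on the cutoff.** Let each control type have SD 1 and means d apart, used half and half. The pooled SD is √(1 + d²/4) and the cutoff is 2.5 times that. For example, at d = 2: √2 = 1.414, and 2.5 × 1.414 = 3.54. With exactly 4 + 4 controls, the sample variance averages 1 + d² × (4 × 4)/(8 × 7). That gives SDs of 1.13, 1.46 and 1.89 at d = 1, 2, 3, slightly more than the large-sample formula.

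**4. False PD response rate, no drug effect.** Simulation with 400,000 replicates and 4 controls of each type. Earlier-tissue controls are d lower, treated tissue behaves like same-operation tissue, and all values are independent. A response is a difference above 2.5 times the pooled sample SD.

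| d | Pooled SD (formula) | Cutoff, within-type SDs | Own control is earlier tissue | Own control is same-operation | Compared with mean of all 8 |
|---|---|---|---|---|---|
| 0 | 1.00 | 2.50 | 5.2% | 5.2% | 2.5% |
| 0.5 | 1.03 | 2.58 | 8.7% | 5.4% | 3.6% |
| 1 | 1.12 | 2.80 | 11.7% | 4.5% | 3.9% |
| 2 | 1.41 | 3.54 | 14.3% | 1.9% | 2.8% |
| 3 | 1.80 | 4.51 | 13.2% | 0.4% | 1.1% |

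Against the mean of all 8, the chance of detecting a true rise of 3 within-type SDs is 68.3% at d = 0, 72.4% at d = 1, 62.8% at d = 2 and 46.1% at d = 3.

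**5. No mixing, but all 8 controls from earlier tissue.** The SD is not inflated. The false rate against the control mean is 2.5%, 6.1%, 12.8% and 37.2% at d = 0, 0.5, 1 and 2.

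**6. Does an offset alone force a response?** In the half-and-half mix this needs d > 2.5√(1 + d²/4), that is d² > 6.25 + 1.5625d², which no d satisfies. The offset never exceeds 2/2.5 = 0.8 of the inflated cutoff.

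**The case against.** The strongest reply is that the earlier-tissue problem depends on Section 3.1. If the infusion takes place during surgery, pre-infusion tumor could come from the same operation, frozen in the same way. That stands as a condition, but it leaves a contradiction in the timing and an undefined control, and both need resolving.

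Three stronger readings are tempting, and the documents do not support them:
- **Paraffin tissue will be compared with frozen tissue.** No section says so. The slides and blocks are described for diagnostic use. The section on PD samples (5.2.1.2) describes −80 °C storage and names a tissue bank. A preservation mismatch is possible, not planned.
- **The two control types will be pooled.** Section 10 gives one SD and no split by type, but one type could be used throughout. The defect is that nothing rules out mixing.
- **A 2.5-SD offset by itself makes a PD response.** Step 6 shows that it cannot in a half-and-half mix. It could if all controls were earlier tissue, or if one type were under about 20% of the set. The general result is a shifted error rate.

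It is also fair to say that tumor PD is secondary, is reported as a frequency with a confidence interval, and has no decision rule attached.

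**Conclusion.** The point holds in a conditional form. As written, Section 10 permits a PD contrast confounded with intervening therapy and tissue handling, and a cutoff computed over unlike controls. With a half-and-half mix and own-control comparison, the false response rate for earlier-tissue patients roughly doubles at d = 1 (11.7% against 5.2%), while same-operation patients face a stricter test. Against the mean of a mixed set the false rate hardly moves, and the cost is lost power at larger d.

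These sizes rest on assumptions: the values of d, 8 controls, an even mix, earlier tissue reading lower, and independence within patient. If earlier tissue read higher, the offset would hide true effects instead. If 8 patients are PD-evaluable, one misclassified patient moves the response frequency by 1/8 = 12.5 points. The primary PK rule does not use these controls and is unaffected.

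**What to change.** 1. Reconcile Sections 3.1, 3.4, 3.7.2, 5.1.1.1, 5.1.2.11 and 10 on when the infusion occurs relative to tissue sampling, and state the source of the pre-infusion control.
2. Designate one control type for the main tumor PD analysis. Do not default to initial-exposure tissue without justification: on the Section 3.1 timing it is itself taken after the infusion. If both types are kept, estimate the SD from deviations within type, use the matching t degrees of freedom, and report PD response frequency by control type.
3. Accept as control only material preserved and assayed by the same method as the treated tissue. Record control type, preservation and intervening therapy.

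The cost is wording in Section 10, reconciled text elsewhere and a few data fields. Section 5.1.2.11.1 has the PD assays batched and run retrospectively, so the rule can be fixed before they are run. There may be fewer PD-evaluable patients and fewer degrees of freedom. With 4 + 4 controls, a within-type SD has 6 degrees of freedom, and comparison with the mean of one type uses 2.447 × √(1 + 1/4) = 2.74 SDs instead of 2.51. With only 5 controls of one type, the two-sided multiplier is 3.04.

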1.1.2 Secondary Objectives

- 1.1.2.1 To determine the concentration LB100 and its major metabolite, 7-oxabicyclo [2.2.1] heptanes-2,3-dicarboxylic acid (LB100M) in glioma tumor tissue when a known non-toxic dose of LB100 is delivered intravenously over 2 hours.
- 1.1.2.2 To determine the PD effect of LB100 in glioma tumor tissue.
- 1.1.2.3 To determine the plasma concentration and calculated PK parameters of LB100 and LB100M (endothall).
- 1.1.2.4 To determine changes in phospho-protein expression in circulating PBMC.
- 1.1.2.5 Intra-patient PD effect in PBMC and tumor tissue will be evaluated in all subjects for presence of correlation to identify potential predictive markers.

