5.1.2.11 Assay Validation

See Appendix **16.3**

Tissue PD effect of LB100 will be performed by assaying phospho-protein expression in glioma tissue resected prior to and after infusion of LB100.

LB100 is a serine/threonine phosphatase inhibitor. Exposure to LB100 results in increased expression of phospho-serine/threonine residues. The antibody we chose to mark LB100 activity detects variety of proteins and peptides phosphorylated at the threonine residues in a manner independent of the surrounding amino acid sequence (Cell Signaling Technology, Phospho-Threonine Antibody (P-Thr-Polyclonal), #9381). Our preclinical studies indicate that expression of phospho-protein (phospho-threonine antibody was used) upon treatment with LB100 is seen at the earliest by 4 hours (Left panel below). By 8-hours expression is reliable, and maintained for approximately 40 hours (Right panel below). Okadaic acid (OA), well-established PP2A inhibitor, was used as positive control.

Abbreviated Title: Phase II Study LB100 gliomas
Version Date: 06/02/2022

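### Tumor PD is summarised only by a per-patient cutoff of 2.5 inter-patient SDs; for same-patient tissue the .05 level does not hold, and a modest consistent rise can be missed

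*Combined protocol and SAP*

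**What the plan says.** Section 10 defines the endpoint: "PD response is defined as statistically significant elevation of phospho-protein expression in treated tumor tissues compared to untreated glioma specimens". It defines control tissue: "Tissue samples obtained with the initial surgical exposure of the tumor OR material obtained prior to LB100 infusion will be used as control". The yardstick is the SD across patients before treatment: "Untreated inter-patient baseline variance of phospho-protein expression and standard deviation (SD) will be calculated". The rule is that a "difference greater than 2.5 times the baseline SD is statistically significant at the .05 significance level", and the t-"distribution is to be used to calculate the cutoff defining the PD response". Neither the degrees of freedom nor the sidedness is given. The only tumor PD result that section 10 then asks for is the frequency of PD response with a 95% confidence interval.

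Section 5.1.2.11 describes the tissue assay as "assaying phospho-protein expression in glioma tissue resected prior to and after infusion of LB100". Read with the control definition, this suggests that each patient supplies both a control and a treated specimen, but no sentence says so. Section 10 names no within-patient SD, mean change or paired test for tumor PD.

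**The concern.** If both specimens come from one patient, the quantity of interest is that patient's change. Whatever makes one tumor's baseline phospho-protein level differ lastingly from another's drops out of the change. Such differences are plausible here: section 2.1.1 admits glioblastoma/gliosarcoma and grade II-III astrocytoma and oligodendroglioma, and section 2.3.2 has no stratification. The SD between patients still contains them, so it can be too wide a ruler for a within-patient change. Reducing each change to yes or no then leaves its size out of the section 10 summary.

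Section 1.2.5 wants PD results in order to confirm target modulation in glioma. At stake is whether a modest but consistent rise would be visible in the planned summary, and whether the stated significance level describes the rule.

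**Working it through.** **Inputs.** From section 10: 8 evaluable patients, cutoff 2.5 baseline SDs, level .05, t-distribution. Assumed, because the documents give neither: the within-patient correlation ρ between control and treated values (0 to 0.8), and the true rise δ, equal in every patient and in units of the between-patient SD. Values are taken as normal with equal variance on the analysis scale.

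**Reproducing the plan's figure.** A two-sided t prediction limit for one treated value against the mean of 8 untreated values is

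t(0.975, 7) × √(1 + 1/8) = 2.508,

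which rounds to 2.5. The plan does not show its derivation, but this match suggests a comparison with pooled controls that treats treated and control values as independent.

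**Same-patient comparison, SD known.** The change has SD √(2(1−ρ)), so

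P(patient passes) = 1 − Φ((2.5 − δ)/√(2(1−ρ))).

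- δ = 0: 1 − Φ(2.5/1.414) = 3.9% at ρ = 0; 1 − Φ(2.5/1) = 0.6% at ρ = 0.5; 1 − Φ(2.5/0.632) = 0.004% at ρ = 0.8.
- δ = 1: 1 − Φ(1.5/1.414) = 14.4%; 1 − Φ(1.5/1) = 6.7%; 1 − Φ(1.5/0.632) = 0.9%.

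**SD estimated from the 8 controls, as planned.** Simulation, 200,000 trials of 8 patients. The last column is the two-sided .05 paired t-test on the same patients, with noncentrality δ√8/√(2(1−ρ)), which is 2.00, 2.83 and 4.47 at δ = 1.

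| ρ | False call, own control (δ = 0) | Pass, own control (δ = 1) | P(0 of 8), own control (δ = 1) | Pass, pooled control mean (δ = 1) | Paired t power (δ = 1) |
|---|---|---|---|---|---|
| 0 | 5.2% | 18% | 26% | 13% | 41% |
| 0.5 | 1.7% | 12% | 49% | 11% | 68% |
| 0.8 | 0.2% | 6% | 75% | 10% | 97% |

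False calls are one-sided, per patient. A result of 0 of 8 has an exact 95% upper limit of 1 − 0.025^(1/8) = 37%.

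**Larger rises.** At δ = 2.5 about 54% of patients pass against their own control, nearly whatever the correlation. At δ = 3 it is 66% to 75% for ρ from 0 to 0.8.

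**Fewer pairs.** With δ = 1 and ρ = 0.5, two-sided paired power falls from 68% with 8 pairs to 29% with 4 and 18% with 3.

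**The case against.** The strongest reply is that same-patient pairing is inferred. The endpoint is worded against untreated specimens in general, and 2.508 is the limit for one treated value against pooled controls. For that comparison the inter-patient SD is the matching yardstick. This stands: a reader might infer that this SD is simply an error, and the documents do not support that. On the pooled reading the false-call rate also depends less on correlation: about 2.5%, 1.7% and 0.8% at 0, 0.5 and 0.8. What remains there is lost efficiency, since only 13% to 10% of patients pass at a 1-SD rise.

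Section 1.1.2 might be cited for pairing: "Intra-patient PD effect in PBMC and tumor tissue will be evaluated in all subjects". It is weak support. Section 5.1.2.11.1 explains that the comparison is between PBMC and tumor within a patient. That section also plans to correlate drug concentrations with PD endpoints, and neither analysis is said to use only the yes/no call. So it cannot be said that the whole plan discards the size of the change, only that section 10's tumor PD summary does.

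A per-patient pass rate and the power of a group-mean test are different quantities. Setting them side by side shows what each summary can reveal, not two powers for one hypothesis.

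Finally, pairs may be scarce. Section 3.1 places the infusion 2 to 4 hours before surgery, and the section 3.4 calendar schedules no pre-infusion tissue procedure. Prior material in section 2.2.1 is slides for diagnostic review, whereas section 5.1.1.2 has treated tissue flash frozen. This also stands and shapes the fix.

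**Conclusion.** The concern holds with limits. If control and treated tissue come from the same patient, the 2.5-SD rule does not have a fixed .05 level: its one-sided false-call rate runs from 5.2% to 0.2% as the correlation goes from 0 to 0.8. A uniform 1-SD rise would be flagged in only 18% to 6% of patients, while a paired analysis of 8 patients would detect it with 41% to 97% power. These figures rest on normality, 8 usable pairs, and an assumed correlation and effect.

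A reader might infer that a real effect in every patient would give a near-zero response rate. That requires both a small rise and a high correlation, and the documents give neither; at a 2.5-SD rise about half the patients respond. Nor does the plan say that 0 of 8 would be declared no PD effect: PD is a secondary objective, section 10 sets no decision threshold on it, and the interval would reach 37%.

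**What to change.** In section 10:

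- State whether control and treated tissue are from the same patient.
- Add, as the main tumor PD summary, the within-patient change log(treated/own control): mean, 95% t-interval and paired t-test, with an exact signed-rank test as a check. Include every patient who has a control specimen of their own as the plan defines control.
- Report results by control type (pre-infusion material, or tissue at initial surgical exposure), with pre-infusion controls only as a sensitivity analysis. Restricting the main analysis to them could leave few pairs.
- Keep the 2.5-SD responder frequency with its interval as descriptive, and drop the claim of significance at .05 for paired tissue.
- Reconcile section 3.1 with the control definition in section 10. With infusion before surgery, tissue at initial exposure is already post-infusion, so using it as untreated control could shrink the measured change.

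The cost is protocol wording and a few lines of analysis, with no specimens beyond those the plan already calls for. The downside is that usable pairs may number fewer than 8, so the number of pairs and the interval width should be reported. Because section 5.1.2.11.1 has the assays batched and run retrospectively, the change should be fixed before those results are analysed.
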